#### 8.1.1 EXPLORATORY EFFECTIVENESS PARAMETERS

The following exploratory effectiveness outcomes will be summarized descriptively based on the observed data. Except for the Quality of Vision Questionnaire (QoV), all the observed data will be summarized for the primary eyes and fellow eyes successfully implanted with RxLAL separately. The summaries will also be performed for all eyes.

##### UCDVA

Number and percent of primary eyes, fellow eyes, and all eyes (i.e. primary and fellow eyes) successfully implanted with the RxLAL with a UCDVA of 20/20 or better at 6 Months Postop (3 Months Post Lock-In) will be presented and the corresponding 95% confidence interval for the percent based on the binomial distribution will be calculated.

UCDVA will be presented with the number and percent of eyes that fall into each category of UCDVA (e.g. 20/20 or better, 20/25 or better, 20/32 or better, etc.) at each visit. The mean UCDVA letter score will be calculated for each visit. Change in UCDVA from Postop Week 3 will be presented at each visit as categorical outcomes of “increase in 15 letters or more”, “Increase in 10-14 letters”, “Increase in 5-9 letters”, “No change”, “Decrease in 5-9 letters”, “Decrease in 10-14 letters”, and “Decrease in 15 letters or more”. The mean change from Postop Week 3 will also be presented.

UCDVA will also be presented with the number and percent of eyes that fall into each category of UCDVA (e.g. 20/20 or better, 20/25 or better, 20/32 or better, etc.) stratified into two bins based on preoperative keratometric cylinder ( $\geq 0.50$  D and  $\leq 1.50$  D) and ( $> 1.50$  D and  $\leq 3.00$  D). The mean UCDVA letter score will be calculated for each of the two defined preoperative keratometric cylinder bins.

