**RXSIGHT, INC.****PROTOCOL NO. CSP-028****A SINGLE CENTER EXPLORATORY STUDY TO EVALUATE UNCORRECTED DISTANCE VISION AND QUALITY OF VISION AFTER LIGHT TREATMENTS OF AN IMPLANTED RXSIGHT LIGHT ADJUSTABLE LENS (RXLAL) WITH THE LIGHT DELIVERY DEVICE (LDD) IN SUBJECTS WITH PREOPERATIVE CORNEAL ASTIGMATISM****1 STUDY SYNOPSIS****STUDY OBJECTIVE**

The objective of this study is to evaluate uncorrected distance vision and quality of vision as measured by the McAlinden QoV questionnaire 3 months following the final lock-in treatment of an implanted RxSight Light Adjustable Lens (RXLAL) with the Light Delivery Device (LDD) in subjects with preoperative keratometric astigmatism. This is an exploratory study. No primary effectiveness endpoints will be defined.

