**STUDY POPULATION**

The study population will consist of up to 150 eyes in up to 75 subjects with 0.50 to 3.00 D of pre-operative keratometric astigmatism implanted with the RxLAL. Approximately 1/2 of the study population should have  $\geq 0.50$  D and  $\leq 1.5$  D of preoperative keratometric astigmatism and approximately 1/2 of the study population should have  $> 1.5$  D and  $\leq 3.00$  D of preoperative keratometric astigmatism. At least 10 eyes should have  $> 2$  D of preoperative keratometric astigmatism.

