**STUDY DESIGN**

A prospective, single center, randomized, exploratory clinical study will be conducted. Subjects will be followed for a 6-month period.

Patients who require cataract extraction and intraocular lens implantation will be screened for eligibility. If it is determined that the patient may be eligible to participate, study staff will explain the study purpose, procedures, risks/benefits and subject responsibilities to the potential participant. Written informed consent will be obtained prior to any study specific testing. The patient is enrolled upon signing the informed consent. If both eyes of a patient meet study eligibility, a pre-determined randomization scheme will be utilized to designate each of the patient's eyes as the primary eye or the fellow eye. If only one eye of a patient meets study eligibility, that eye will automatically be designated as the primary eye.

At 3 weeks post-implantation, eyes will be refracted, undergo visual testing, and receive a power adjustment based on the manifest refraction. Subjects will return 3 to 7 days after their adjustment and the same measurements performed again. Depending on the adjustment(s) performed, subjects will receive one to three adjustments and one or two lock-in treatments.

Postoperatively, subjects will undergo complete ophthalmic examinations at regular intervals over a 6-month period.

Uncorrected distance visual acuity (UCDVA) and responses from the Quality of Vision (QoV) questionnaire will be summarized. All ocular adverse events (device related and unrelated) during the conduct of the study will be reported. All Secondary Surgical Interventions (SSIs) in study eyes during the conduct of the study will also be reported.

Both eyes of all subjects should be screened for eligibility.

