## 7.2 SUBJECT ENTRY

Patients who require cataract extraction and intraocular lens implantation will be screened for eligibility. If it is determined that the patient may be eligible to participate, study staff will explain the study purpose, procedures, risk/benefits and subject responsibilities to the potential participant. Written informed consent will be obtained prior to any study specific testing. The patient is enrolled upon signing the informed consent. The subject will sign and date the informed consent form in the presence of the person conducting the consent process. The investigator and/or the person conducting the consent process will also sign and date the consent form. The preoperative examination will be performed no more than 90 days prior to surgery. If the 90-day time period elapses, it is acceptable for patients to be re-screened by undergoing a complete preoperative examination. If both eyes of a patient meet study eligibility, a pre-determined randomization scheme will be utilized to designate each of the patient's eyes as the primary eye or the fellow eye. If only one eye of a patient meets study eligibility, that eye will automatically be designated as the primary eye.

Only subjects meeting all inclusion/exclusion criteria will be implanted. Those subjects who do not meet the inclusion/exclusion requirements will be considered screen failures. Subjects will continue to be enrolled until approximately 150 eyes in about 75 subjects have undergone implantation. Unique identification numbers will be assigned to each subject.

Study enrollment will be tracked to ensure that approximately 1/2 of the study population will have  $\geq 0.50$  D to  $\leq 1.5$  D of preoperative keratometric astigmatism and approximately 1/2 of the study population will have  $>1.5$  D to  $\leq 3.00$  D of preoperative keratometric astigmatism. At least 10 eyes should have  $>2$  D of preoperative keratometric astigmatism. Implantations in one bin may be suspended to ensure enrollment in all bins meets these requirements.

The implant lens power for the RxLAL will be calculated based upon the ocular biometry data and a lens power formula of the surgeon's choice with a postoperative spherical

equivalent (SE) outcome closest to emmetropia. If both eyes of a patient are enrolled, the primary eye will be scheduled for implantation prior to the fellow eye.

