The RxLAL must be implanted following specific surgical procedures. If these procedures are not followed by the surgeon, the lens may become scratched or improperly placed in the eye and may need to be explanted prior to light treatments. In order to perform the lens adjustment or the lens lock-in procedures, the subject's pupil needs to be adequately dilated. If this cannot be accomplished for any reason, additional eye drops, injections into the eye, or surgery may need to be utilized to adequately dilate the pupil. If the pupil cannot be adequately dilated after these types of treatments, the RxLAL may need to be explanted. An unpredicted change in vision can occur resulting from ocular exposure to daylight or any other UV source before the RxLAL is locked-in. The light treatments may not improve vision and/or manifest refraction, and the adjustment/lock-in procedure may make vision worse, such that it may be necessary to remove and replace the RxLAL. Vision loss may be permanent and may not be improved by replacing the RxLAL. There is a potential risk for UV-induced damage to the eye, including the cornea and retina, which may be permanent. UV light can sometimes cause a reactivation of previous herpes virus infection in the eye. A reactivation of herpes virus can cause scarring of the cornea, blurred vision, eye pain, extreme light sensitivity, permanent loss of vision, and possible need for corneal transplant. Temporary or persistent erythropsia and/or temporary or persistent color vision deficiency may occur. Corneal dryness and corneal abrasions from the lens used for adjustment and lock-in can occur. After the lens adjustment(s) or after the lens lock-in procedures, discomfort, itching and light sensitivity may occur. In cases where a spherocylinder adjustment is performed, it is possible that visual disturbances may occur if the IOL rotates or if the correction is not performed on the correct axis of astigmatism.

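### The binomial 95% interval for all eyes treats a subject's two eyes as independent, so it overstates precision if they are more than slightly positively correlated

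*Combined protocol and SAP*

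**What the plan says.** Section 8.1.1 (UCDVA) plans the number and percent of eyes reaching 20/20 or better at the 6-month visit for three sets: primary eyes, fellow eyes, and "all eyes (i.e. primary and fellow eyes) successfully implanted with the RxLAL". For each, "the corresponding 95% confidence interval for the percent based on the binomial distribution will be calculated". The kind of binomial interval (exact, normal approximation or other) is not named. The opening of Section 8.1.1 confirms the pooling: "The summaries will also be performed for all eyes".

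The population is given as "up to 150 eyes in up to 75 subjects" (Sections 1 and 6), and Section 7.2 sets the target: "Subjects will continue to be enrolled until approximately 150 eyes in about 75 subjects have undergone implantation". If that target is met, nearly every subject contributes two eyes. Unilateral subjects are possible: "If only one eye of a patient meets study eligibility, that eye will automatically be designated as the primary eye" (Sections 1, 4 and 7.2). Their expected number is not given.

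Nothing in Section 8 mentions within-subject correlation, a cluster-robust variance, a design effect or resampling by subject.

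**The concern.** A binomial count needs independent units. Two eyes of one person share age, systemic health and behaviour, including compliance with the UV-protective spectacles. Section 9.2.5 warns that "An unpredicted change in vision can occur resulting from ocular exposure to daylight or any other UV source before the RxLAL is locked-in". Poor compliance could plausibly affect both eyes. It is therefore reasonable to expect the two 20/20 outcomes to be positively correlated, although this is an inference and the documents give no value.

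With positive correlation, 150 paired eyes carry less information than 150 independent ones. The pooled interval then claims more precision than the data support. The 20/20 percent is the only effectiveness parameter listed in Section 5.1. The pooled row also has the largest n and the narrowest interval, so it is a natural one to quote.

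**Working it through.** **Inputs from the documents.** 95% level, binomial method, pooled eyes (Section 8.1.1); about 150 eyes in about 75 subjects (Sections 6 and 7.2). The plan states no expected rate, interval width or sample-size calculation, so there is no figure of its own to reproduce.

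**Assumptions.**
- True rate p from 0.70 to 0.90. The 88% used as an example comes from the post-CE-mark study summarised in Section 2.1 and is not a planning value.
- Correlation ρ of the yes/no outcome within a subject: 0.1, 0.3, 0.5 or 0.7.
- Exact (Clopper-Pearson) interval, since no type is named.
- Either 75 bilateral subjects, or 60 bilateral plus 15 unilateral (135 eyes).

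**Step 1: variance.** With 75 pairs and q = 1 − p, the variance of the pooled percent is pq(1 + ρ)/150, against the binomial pq/150. The correct width is therefore √(1 + ρ) times the planned one. In the mixed case, 120 of 135 eyes are paired and the factor is √(1 + ρ × 120/135).

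| ρ | 75 pairs | 60 pairs + 15 single eyes |
|---|---|---|
| 0.1 | 1.05 | 1.04 |
| 0.3 | 1.14 | 1.13 |
| 0.5 | 1.22 | 1.20 |
| 0.7 | 1.30 | 1.27 |

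**Step 2: example at 88%.** For 132/150 the exact interval is 81.7% to 92.7%, a half-width of 5.5 points. Multiplied by the factors for 75 pairs, the half-width becomes about 5.8, 6.3, 6.8 and 7.2 points. For comparison, 66/75 primary eyes (also 88%) gives 78.4% to 94.4%.

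**Step 3: coverage.** For one pair, with c = ρpq, P(both) = p² + c, P(neither) = q² + c and P(exactly one) = 2(pq − c). At p = 0.88 and ρ = 0.3, c = 0.3 × 0.88 × 0.12 = 0.0317, and the three probabilities are 0.806, 0.046 and 0.148. Convolving 75 such pairs gives the exact distribution of the count. Coverage is the probability that the interval contains p. Averages over p = 0.70 to 0.90 in steps of 0.005, with the range for 75 pairs:

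| ρ | 75 pairs | Range over p | 60 pairs + 15 single eyes |
|---|---|---|---|
| 0 | 96.1% | 95.1–97.2% | 96.1% |
| 0.1 | 95.1% | 94.0–96.3% | 95.3% |
| 0.3 | 93.0% | 91.6–94.5% | 93.4% |
| 0.5 | 90.8% | 89.2–92.6% | 91.5% |
| 0.7 | 88.6% | 86.9–90.6% | 89.5% |

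The exact interval is conservative at ρ = 0, and that margin absorbs a correlation of about 0.1 but not 0.3. A normal-approximation interval has no such margin: with 75 pairs it averages 94.3, 93.0, 90.5, 88.1 and 85.6% at the five values of ρ.

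**Step 4: which correlations are plausible.** Dichotomising weakens correlation. Under a bivariate-normal model, correlations of 0.5, 0.7 and 0.9 in underlying acuity give 0.25–0.32, 0.41–0.48 and 0.65–0.70 for the yes/no outcome over these rates. A value of 0.7 is therefore an extreme case.

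**Step 5: does the proposed interval work?** A GEE logit interval was simulated 100,000 times at each of five rates (0.70 to 0.90) and five correlations (0 to 0.7), in both designs. It used an independence working correlation, robust variance times m/(m − 1), and a t quantile on m − 1 degrees of freedom, with m the number of subjects. Coverage was 95.0–96.0% throughout, including at zero correlation.

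**The case against.** The strongest objection is that little depends on this interval. The protocol says "No primary effectiveness endpoints will be defined", the outcomes are descriptive, and no test, margin or success rule uses the pooled row. The pairing is also partly handled by design. When both eyes qualify, primary and fellow eyes are designated by a randomization scheme and reported separately, so a reader already has valid one-eye-per-subject intervals. This stands, and it limits the seriousness of the point. It does not make the pooled interval correct, and the plan neither names the primary-eye row as the main one nor warns readers about the pooled row.

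A second objection is that the size rests on a correlation the documents do not give. Section 9.2.5 does not say that UV exposure affects both eyes together. Requiring every eye to have 20/20 potential and allowing up to three adjustments could lower the correlation. This also stands: at 0.1 with an exact interval the error is negligible, and at 0.3 average coverage is still 93.0%.

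Third, the enrolment figures in Section 6 are ceilings, and more unilateral subjects would shrink the effect. With 40 bilateral and 35 unilateral subjects, average coverage at correlation 0.3 is 94.2%. However, Section 7.2 aims for about 150 eyes in about 75 subjects, so mostly bilateral enrolment is what is planned.

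**Conclusion.** The concern holds for the all-eyes interval only. The rule as written applies an independence-based method to paired eyes. Under any positive correlation the true variance exceeds the one used, and coverage drops below the stated 95% once the correlation is more than slight. For correlations of 0.3 to 0.5, average coverage is about 93% to 91% and the interval should be roughly 14% to 22% wider. This assumes 75 bilateral subjects, true rates of 70–90% and an exact interval. The shortfall is smaller with more unilateral subjects and larger with a normal-approximation interval. The primary-eye and fellow-eye intervals and all point estimates are unaffected. It should be fixed because the reported precision is wrong and the remedy is trivial, not because any decision turns on it.

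**What to change.** Keep the binomial interval for the primary-eye and fellow-eye rows. In Section 8.1.1 (UCDVA), add for the pooled row: *The 95% confidence interval for all eyes will allow for two eyes per subject, using a GEE logit model with subject as cluster and robust variance.* To match what was simulated, also state the independence working correlation, the m/(m − 1) factor and the t quantile on m − 1 degrees of freedom. Omitting the last two matters little: plain robust variance with a normal quantile covered about 94.8–96.0% in a check. A bootstrap that resamples subjects is a reasonable alternative, but its coverage was not tested here.

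The cost is a sentence of text and a few lines of code, with no new data. There are two downsides. The all-eyes interval will be somewhat wider if the eyes are positively correlated. The logit interval does not exist if every eye reaches 20/20; the plan should say that only the two one-eye-per-subject intervals would then be given.

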##### Quality of Vision Questionnaire

Results of the Quality of Vision Questionnaire will be summarized descriptively for subjects bilaterally implanted with the RxLAL and for subjects with the RxLAL implanted only in the

primary eye preoperatively, at Postop Week 3, 1 Month Post Lock-In, and at 6 Months Postop (3 Months Post Lock-In).

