## 6 STUDY POPULATION

The study population will consist of up to 150 eyes in up to 75 subjects with 0.50 to 3.00 D of pre-operative keratometric astigmatism implanted with the RxLAL. Approximately 1/2 of the study population should have  $\geq 0.50$  D and  $\leq 1.5$  D of preoperative keratometric astigmatism and approximately 1/2 of the study population should have  $> 1.5$  D and  $\leq 3.00$  D of preoperative keratometric astigmatism. At least 10 eyes should have  $> 2$  D of preoperative keratometric astigmatism.

Both eyes of all subjects should be screened for eligibility.

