#### 7.4 EXAMINATION SCHEDULE

Subjects who agree to participate in the study will return for the listed follow-up examinations for each study eye:

Evaluation	
Preoperative	Day -90 to Day -1
Operative	Day 0, day of surgery
Postop Day 1	Days 1 to 2 postop
Postop Week 1	Days 7 to 14 postop
Postop Week 3	Days 17 to 24 postop: Adjustment #1
Adjustment #2, if needed	3 to 7 days post Adjustment #1
Adjustment #3, if needed	3 to 7 days post Adjustment #2
Lock-in #1	3 to 7 days post final adjustment
Lock-in #2, if needed	3 to 7 days post lock-in #1
Post Lock-In	3 to 7 days post final lock-in
1 Month Post Lock-In	30 to 60 days post final lock-in
3 Months Post Lock-In/6 Months Postop	Days 120 to 180 postop

Unscheduled visits falling outside the designated ranges for scheduled visits will be considered “interim” visits for data recording purposes and a report form will be completed.

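### Does the Postop Week 3 Quality of Vision summary for bilaterally implanted subjects need a rule saying which eye's visit it uses?

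*Combined protocol and SAP*

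**What the plan says.** Section 8.1.1 (Exploratory Effectiveness Parameters) treats the questionnaire differently from every other outcome: "Except for the Quality of Vision Questionnaire (QoV), all the observed data will be summarized for the primary eyes and fellow eyes" separately. Under its Quality of Vision heading the unit becomes the subject: "Results of the Quality of Vision Questionnaire will be summarized descriptively for subjects bilaterally implanted with the RxLAL", with a second group of subjects implanted in the primary eye only. The time points are preoperative, Postop Week 3, 1 Month Post Lock-In and 6 Months Postop (3 Months Post Lock-In).

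Visits, however, belong to eyes. Under section 7.4 subjects "return for the listed follow-up examinations for each study eye", and the Postop Week 3 entry reads "Days 17 to 24 postop: Adjustment #1". Section 7.2 fixes the order of the surgeries: "the primary eye will be scheduled for implantation prior to the fellow eye". It gives no interval. The nearest limit is indirect. Section 6 says "Both eyes of all subjects should be screened for eligibility", and section 7.2 says "The preoperative examination will be performed no more than 90 days prior to surgery", with re-screening allowed after that.

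Sections 1 and 3 name quality of vision, measured 3 months after final lock-in, as one of two things the study evaluates. They also say the study is exploratory and has no primary effectiveness endpoint. Section 7.5 refers the assessment schedule to Table 2 and the methods to a techniques reference. In the public text the Table 2 grid is not shown and the reference is redacted.

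**The concern.** A questionnaire answered once by a person is tied to a visit that happens once per eye. The readable text of section 8.1.1 does not say whose Week 3 visit supplies the record, or whether the questionnaire is given at both.

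The choice would not be neutral. Week 3 is when the first light adjustment is scheduled, and the same section uses it as the reference for change in uncorrected distance acuity. A reader could easily take the bilateral QoV row as the state before adjustment in both eyes and compare it with the rows after lock-in. If the second surgery came more than a week after the first, the row would instead describe subjects with one eye at Week 3 and the other unoperated, recently operated or already past its first adjustment window. A target of about 150 eyes in about 75 subjects is two eyes per subject, so bilateral subjects would be most of the sample. Without a stated rule, the visit could also be picked after the answers are known.

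**Working it through.** The plan gives no figure to reproduce here. The check is on visit windows.

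**Inputs.**
- Week 3 is Days 17 to 24 after that eye's surgery (section 7.4).
- Treatments are 3 to 7 days apart, with one to three adjustments and one or two lock-ins (sections 7.3.2 and 7.4).
- 1 Month Post Lock-In is 30 to 60 days after final lock-in, and the final visit is Days 120 to 180 (section 7.4).
- The gap between surgeries, g days, is an assumption, because the readable text does not state it.

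**Range of g.** With one shared preoperative examination at least 1 day before the first surgery and at most 90 days before the second, g can reach 90 − 1 = 89. On the synopsis window of Day −60 it can reach 60 − 1 = 59. This shows what is permitted, not what is planned.

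**Week 3.** On the primary eye's clock the two windows are 17 to 24 and 17 + g to 24 + g. They share max(0, 8 − g) days. At the primary eye's Week 3 the fellow eye is at Day 17 − g to 24 − g. At the fellow eye's Week 3 the primary eye is at Day 17 + g to 24 + g.

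| g (days) | Shared Week 3 days | Fellow eye's day at primary Week 3 | Primary eye's day at fellow Week 3 |
|---|---|---|---|
| 0 | 8 | 17 to 24 | 17 to 24 |
| 7 | 1 | 10 to 17 | 24 to 31 |
| 8 | 0 | 9 to 16 | 25 to 32 |
| 14 | 0 | 3 to 10 | 31 to 38 |
| 21 | 0 | −4 to 3 | 38 to 45 |
| 25 | 0 | −8 to −1 | 42 to 49 |

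The threshold of 8 days is exact. A gap of 7 days or less makes a shared date possible, not certain. The fellow eye may be unoperated at the primary eye's Week 3 once g exceeds 17, and always is once g exceeds 24.

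**Final visit.** Final lock-in is scheduled between Day 17 + 3 = 20 and Day 24 + 7 + 7 + 7 + 7 = 52. At the primary eye's final visit the fellow eye is 120 − g − 52 = 68 − g to 180 − g − 20 = 160 − g days past its own final lock-in. That is 54 to 146 days at g = 14 and 40 to 132 days at g = 28. The lower bound stays at 0 or above up to g = 68. The two final windows share at least one date up to g = 180 − 120 = 60.

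**1 Month Post Lock-In.** This falls on Day 20 + 30 = 50 to Day 52 + 60 = 112. At the primary eye's visit with g = 28 the fellow eye is at Day 22 to 84, against a final lock-in on Day 20 to 52, so it may not yet be locked in. The two eyes can still share a date for this visit if their final lock-ins are no more than 60 − 30 = 30 days apart.

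**Would a fixed rule for every time point help?** Suppose Week 3 came from the primary eye's visit and the post-lock-in rows from the second eye's visit. At g = 28 the primary eye would be at Day 120 + 28 = 148 to 180 + 28 = 208 when the final questionnaire is completed, which can fall outside its own window of Days 120 to 180. The rows would also run on different clocks. Splitting the Week 3 row into unoperated, unadjusted and adjusted fellow eyes would leave the last group empty on schedule when g is 8 or more: the fellow eye is then at Day 24 − 8 = 16 at the latest, before its earliest adjustment on Day 17.

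**The case for a change.** The strongest case for a change is that section 8.1.1 is itself fully readable and contains no rule. Quality of vision is in the study objective, sequential surgery is built into section 7.2, and a short statement would cost almost nothing. Even if Table 2 names the visit, the windows still fail to overlap at gaps of 8 days or more, so the other eye's status would remain unreported.

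Most of this stands as description. The non-overlap is real, and a report that printed the bilateral Week 3 row without comment could mislead. Three things keep it from being a defect in the plan. First, the visits at which the questionnaire is given would normally be set in the schedule grid or the techniques reference. Neither can be read, so their content cannot be counted as absent. Second, the plan never says the row represents two eyes before adjustment. It plans change from Week 3 for acuity and none for QoV, so the misleading comparison is one a reader would bring to the table. Third, the information needed to label the row should already be held: visits run per eye, each eye's Day 0 is its surgery date, sections 7.3.2.3 and 7.3.2.4 call for light treatments to be recorded, and section 7.6 puts study data on case report forms.

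**Conclusion.** No change to the plan is called for. The observation is correct within its condition: at a gap of 8 or more days, the Postop Week 3 QoV row for bilaterally implanted subjects cannot show both eyes at Week 3. The gap is not stated in the readable text, so the share of subjects affected could be anything from none to all bilateral subjects, of whom there are at most 75.

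The consequence is limited to how a descriptive row is read. No test, interval or change score rests on it. The 3-month time point named in the objective is not undermined; on scheduled windows, what differs between the eyes there is mainly time since lock-in. The 1 Month row can be touched at longer gaps, but its windows are wide enough for the eyes to share a date in many cases.

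This is a gap that analysts fill sensibly. When the table is produced, a footnote can say which eye's Week 3 visit supplied the record and how many other eyes were unoperated, or implanted and not yet adjusted, if the primary eye's visit is used. A rule for every time point would bring timing mismatches of its own for no clear gain.

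The conclusion assumes that visits keep to their windows, that surgery and treatment dates are on file, and that QoV stays descriptive. If Week 3 QoV were later used as a baseline for a change score or a comparison, the source visit would have to be fixed in advance.
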